Eligible patients will undergo one 8-week treatment period, during which time they are randomized to take IX-01, 400, 800, or 1200 mg or matching placebo. In order to maintain the double-blind, each dose will be presented as 3 caplets in blisters in single-dose units. Thus, for example, a patient randomized to 400 mg IX-01 will receive blister cards with each dose comprising one IX-01 400 mg caplet and two matching placebo caplets. Patients will complete an e-diary (LogPad) on all days during the treatment period that sexual activity is performed with or without the use of the study drug.

During the treatment period, patients will be expected to return to the study site and use their LogPad to complete the following questionnaires according to the study schedule:

- Premature Ejaculation Profile (PEP)
- International Index of Erectile Function (IIEF)
- Patient Health Questionnaire (PHQ-9)
- Patient Global Impression of Severity (PGIS)
- Clinical Global Impression of Change (CGIC) – Early Termination/Visit 5 only

The LogPad will provide results to the Investigator regarding whether or not the patient is required to complete the C-SSRS. The C-SSRS is mandatory at baseline, and is only mandatory at all other visits if the PHQ-9 total score is >9 , and/or the PHQ-9 Question 9 score is >0 ; it may also be administered at any time if clinically indicated, in the opinion of the Investigator. A final follow-up visit is conducted 2 weeks after the end of double-blind treatment. For more details of the procedures at each study visit, please refer to Section 6.

4 Patient Selection and Withdrawal Criteria

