4.2 Withdrawal of Patients From the Study

Patients will be discontinued from the investigational product and/or from the study in the following circumstances:

1. Enrollment in any other clinical study involving an investigational product or enrollment in any other type of medical research judged not to be scientifically or medically compatible with this study.
2. The patient requests to be discontinued from the study.
3. Sponsor decision to stop the study or to stop the patient's participation in the study for medical, safety, regulatory, or other reasons consistent with applicable laws, regulations, and Good Clinical Practice (GCP).
4. If a clinically significant event occurs that is considered related to the study drug, then the investigational product is to be discontinued and appropriate measures taken. A clinically significant event will be defined as a moderate to severe AE (eg, rash), abnormal clinical sign, or clinical laboratory finding that may pose a risk to the well-being of the patient.

5. The results of the PHQ-9 and C-SSRS indicate a change in mental condition and a risk to the patient by continuing in the study. (see Section 13.2)
6. Certain laboratory test criteria are fulfilled:
 - a. Discontinuation of the investigational product for abnormal liver tests must occur when a patient meets one of the following conditions after consultation with the designated medical monitor:
 - i. Alanine aminotransferase (ALT) or aspartate aminotransferase (AST) $>8 \times$ ULN
 - ii. ALT or AST $>5 \times$ ULN for more than 2 weeks
 - iii. ALT or AST $>3 \times$ ULN and total bilirubin level $>2 \times$ ULN or prothrombin time $>1.5 \times$ ULN
 - iv. ALT or AST $>3 \times$ ULN with the appearance of fatigue, nausea, vomiting, right upper-quadrant pain or tenderness, fever, rash, and/or eosinophilia ($>5\%$)
 1. Liver function tests should be repeated if ALT and or AST $>3 \times$ ULN and/or bilirubin $>1.5 \times$ ULN (or $1.5 \times$ baseline value if baseline value was $>ULN$)

The nature of any conditions, clinical signs or symptoms, or abnormal laboratory values present at the time of discontinuation and any applicable follow-up procedures will be documented. Patients who are discontinued early from the study should complete the Early Termination visit (see Section 6.1). Every effort will be made to follow up all patients for safety.

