- The patients who meet all of the eligibility criteria will be randomized and assigned a treatment number. Eligible patients will be provided with at least 7 doses of study drug (IX-01 or placebo). Further supplies can be dispensed at this visit based on a discussion between the Investigator and patient but the maximum allowed dose is 1 dose (3 caplets) per day. Each dose of study drug comprises 3 caplets contained within a discrete blister card. Patients must be informed that 1 dose is all 3 caplets, and the dose should be taken with water at least one hour before or after food. Patients should attempt sexual intercourse approximately 1 to 6 hours after taking the dose. The patients will also be provided with a LogPad. Patients should be reminded on the instructions for using the stopwatch and also the LogPad to record their usage of the study medication, as well as all occasions that they attempt sexual intercourse and whether alcoholic drinks were

taken. Patients will be asked if they are willing to try intercourse with their partner approximately 8 times or more between Visit 2 and Visit 5 although less than 8 attempts will not be classified as a protocol deviation. Patients should be reminded to bring their LogPad and any unused study medication back to the study site for Visit 3.

Visit 3

- Patients will return to the study center on Day 14 \pm 3 days (Week 2). The patients will be asked for information on any AEs that have occurred or are occurring and concomitant medication usage since Visit 2. The remaining study medication will be collected, and a check of the quantity remaining will be performed. After completion of all assessments, the patient will receive enough medication to take at least 7 doses of study drug (IX-01 or placebo). Further supplies can be dispensed at this visit based on a discussion between the Investigator and patient but the maximum allowed dose is 1 dose (3 caplets) per day. (Note: Refer to the Study Training Manual for instructions if a patient does not remember to return the LogPad.)
- The patient will return the LogPad.
- The investigator will provide the LogPad back to the patient for completion of the PHQ-9. Once complete, the patient will return the LogPad to the investigator.
- If the results of the PHQ-9 indicate a change in mental condition and/or if the investigator suspects a deleterious change in mood (see Section 13.2), the investigator must administer the C-SSRS.

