- Physical examination. Any changes in physical findings that meet the definition for an AE and that occur after the patient initiates investigational product will be recorded as AEs in the eCRF.
- Blood sampling for laboratory safety tests (including hematology and clinical chemistry analyses).
- Adverse events and concomitant medication update.

Visit 4

- Patients will return to the study center on Day 28 \pm 7 days (Week 4). The patients will be asked for information on any AEs that have occurred or are occurring and concomitant medication usage since Visit 3. The remaining study medication will be collected, and a check of the quantity remaining will be performed. After completion of all assessments, the patient will receive enough medication to take at least another 14 doses of study drug (IX-01 or placebo). Further supplies can be dispensed at this visit based on a discussion between the Investigator and patient but the maximum allowed dose is 1 dose (3 caplets) per day. (Note: Refer to the Study Training Manual for instructions if a patient does not remember to return the LogPad.)
- The patient will return the LogPad.
- The investigator will provide the LogPad back to the patient for completion of the PEP, PGIS, IIEF, and PHQ-9. Once complete, the patient will return the LogPad to the investigator.
- If the results of the PHQ-9 indicate a change in mental condition (or the investigator suspects an adverse change), the investigator should administer the C-SSRS and determine if the patient may remain in the study.
- Physical examination.
- Recording of vital signs data (heart rate and blood pressure measurements).
- Blood sampling for laboratory safety tests (including hematology and clinical chemistry analyses).
- Urinalysis.
- Adverse events and concomitant medication update.

Visit 5 (End of Treatment or Early Termination)

Note that if a patient is discontinued from the study at any time during the treatment period earlier than expected, then he must return to the study site and complete an early termination visit (Visit 5).

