- Patients will return to the study center on Day 56 ± 7 days (Week 8). The patients will be asked for information on any AEs that occurred or are occurring and concomitant medication usage since Visit 4. The patient must return the LogPad. The remaining study medication will be collected. The LogPad will be checked and retained at the study center. (Note: Refer to the Study Training Manual for instructions if a patient does not remember to return the LogPad.)
- The investigator will provide the LogPad back to the patient for completion of the PEP, IIEF, PHQ-9, PGIS and CGIC. After completion, the patient will return the LogPad to the investigator.
- If the results of the PHQ-9 indicate a change in mental condition (or the investigator suspects an adverse change), the investigator should administer the C-SSRS.
- Weight.
- Physical examination.
- Recording of vital sign data (heart rate and blood pressure measurements) and 12-lead ECG.
- Blood sampling for laboratory safety tests (including hematology and clinical chemistry analyses).
- Urinalysis.
- Urine drug screen.
- Adverse events and concomitant medication update.

End of Study Visit 6 (Follow Up)

Patients will return to the study center for a follow-up visit on Day 70 \pm 7 days (Week 10), and the following assessments will be performed approximately 2 weeks after the last visit:

- Weight.
- Physical examination.
- Recording of vital sign data (heart rate and blood pressure measurements) and 12-lead ECG.
- Blood sampling for laboratory safety tests (including hematology and clinical chemistry analyses).
- Urinalysis.
- Adverse events and concomitant medication update.
- C-SSRS, only if clinically indicated per the protocol.

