Laboratory Safety Tests: Hematology and clinical chemistry safety tests will be summarized by treatment and visit. Postbaseline visit will include change from baseline. Shift tables displaying baseline versus worst postbaseline results will be provided by treatment group.

PHQ-9: The PHQ-9 is comprised of 9 questions and is used to monitor depression symptoms. All questions elicit responses on an ordered 4-point scale (0-3), which are added together to generate a single summary score. Higher summary scores indicate an increase in depression severity. The questionnaire is administered at baseline, Week 2, Week 4, and Week 8 visits. Total PHQ-9 scores will be summarized by treatment and visit, with the postbaseline visit displaying raw values as well as change from baseline. In addition, responses to the final question “If you checked off any problems, how difficult have these problems made it for you to do your work, take care of things at home, or get along with other people?” will be summarized by visit as frequency data.

Columbia-Suicide Severity Rating Scale (C-SSRS): The C-SSRS is a structured clinical interview used to assess an individual’s behavior to exhibit thoughts or intent to commit suicide. The questionnaire will be completed at baseline and may be administered at other visits thereafter if clinically indicated. Baseline results will be summarized and listed. Postbaseline results will be listed.

International Index of Erectile Function (IIEF): The IIEF is a questionnaire that comprises 15 questions assessing the effect that erection problems have had on the patient’s sex life over the previous 4 weeks. It is administered at baseline, Week 4, and Week 8. Summary statistics will be provided by visit, and questionnaires will be listed in detail.

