2. Refer to the Study Training Manual for instructions if a patient does not remember to return the LogPad.
3. The patient will return the LogPad to the investigator. The LogPad will provide a summary of the IELT data collected during the run-in period, and will indicate whether the patient is eligible to continue in the study based on the IELT criteria
4. Coagulation (prothrombin time and activated partial thromboplastin time) will be tested at baseline (Visit 2). Only prothrombin time will be taken at other time points if certain laboratory test criteria defined in Section 4.2 are fulfilled.
5. Medication use, IELT, ejaculation control, and ejaculation-related distress and alcohol intake are collected after each event via e-diary.
6. IIEF and PEP have 4-week recall periods, and so these questionnaires are completed by the patients at study visits as above.
7. Columbia-Suicide Severity Rating Scale is only mandatory at baseline but may be administered at other visits if clinically indicated.

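### Section 3.1 makes the post-baseline suicidality interview mandatory on a PHQ-9 trigger, but the Schedule of Events and Section 7.6.3 make it optional, so the passages must be reconciled

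*Combined protocol and SAP*

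**What the plan says.** Section 3.1 states the rule with numbers: "The C-SSRS is mandatory at baseline, and is only mandatory at all other visits if the PHQ-9 total score is >9". It adds a second trigger, a Question 9 score above 0. It then gives a separate route at any time, at the Investigator's discretion, when the interview is clinically indicated. It also says that the LogPad will tell the Investigator whether the interview is required.

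Footnote 7 of Table 13-1 (Section 13.1) reads: "Columbia-Suicide Severity Rating Scale is only mandatory at baseline but may be administered at other visits if clinically indicated". Section 7.6.3 says that the instrument is completed at baseline and "may be administered at other visits thereafter if clinically indicated". Neither mentions the PHQ-9 trigger.

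Section 6.1 words it visit by visit, conditional on PHQ-9 results pointing to a changed mental state or on the investigator's own suspicion:
- Visit 3: "the investigator must administer the C-SSRS"
- Visit 4: "the investigator should administer the C-SSRS and determine if the patient may remain in the study"
- Visit 5: the weaker verb again (should), without the clause on remaining in the study
- Visit 6: "C-SSRS, only if clinically indicated per the protocol"

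In Section 4.2, withdrawal criterion 5 begins: "The results of the PHQ-9 and C-SSRS indicate a change in mental condition and a risk to the patient".

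**The concern.** The interview is the follow-up to a positive depression or suicidality screen. If one current passage requires it and another says that it is not required, a site can omit it and point to the protocol in its defence. A monitor could record the same omission as a deviation under Section 3.1 and as compliance under the schedule.

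The patients affected are the ones the screen is meant to find. Exclusion criterion 23 bars anyone with a PHQ-9 total above 9 or a Question 9 score above 0. A correctly enrolled patient who meets the Section 3.1 trigger after baseline has therefore newly crossed the protocol's own entry limit.

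Withdrawal criterion 5 is worded on the results of both instruments, so a skipped interview leaves it without one of them. Section 7.6.3 plans only a listing of post-baseline C-SSRS results and describes no output that matches positive screens to interviews. An omission would not show up in the planned safety summaries.

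**Working it through.** No figure is involved, so the check is a comparison of every current passage that sets when the C-SSRS is given. The amendment log is left out. The question put to each passage is what it requires for a patient whose PHQ-9 total is above 9, or whose Question 9 score is above 0, after baseline.

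| Place | Status of the interview | Trigger stated |
|---|---|---|
| Section 3.1 | Mandatory | PHQ-9 total >9 and/or Question 9 >0 |
| Section 6.1, Visit 3 | Must | Changed mental state on PHQ-9, or suspected mood change; no score |
| Section 6.1, Visits 4 and 5 | Should | Same kind of condition; no score |
| Section 6.1, Visit 6 | Only if clinically indicated | No PHQ-9 scheduled |
| Section 6.3 | As the protocol requires | None stated there |
| Section 7.6.3 | May | Clinical indication |
| Table 13-1, footnote 7 | Not mandatory after baseline; may | Clinical indication |

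**Step 1. Is footnote 7 only a short form of Section 3.1?** No. By limiting the mandate to baseline, it denies the conditional mandate that Section 3.1 sets for later visits.

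**Step 2. Could clinical indication include a positive PHQ-9?** Not as Section 3.1 is written. There the clinically indicated route is an addition to the PHQ-9 trigger and rests on the Investigator's opinion. Two routes listed separately, one mandatory and one discretionary, cannot be the same rule.

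**Step 3. Does Section 6.1 settle the matter?** Only in part. It points in the direction of Section 3.1, but the verb weakens after Visit 3 and no score is given. Visit 3 and withdrawal criterion 5 both refer the reader to Section 13.2. That section reproduces the PHQ-9 and C-SSRS forms and contains no threshold for action.

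**Step 4. At which visits can the conflict arise?** Section 7.6.3 and Table 13-1 place the PHQ-9 at baseline and Weeks 2, 4 and 8. The baseline interview is mandatory everywhere. The conflict therefore arises at Weeks 2, 4 and 8, which are Visits 3, 4 and 5.

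**The case against.** The strongest reply is that the protocol already has a working safeguard. The PHQ-9 is completed on the LogPad at Visits 3, 4 and 5, and Section 3.1 says that the device reports whether the interview is required. A positive screen should then be flagged whichever footnote the site has read. Section 3.1 also sends the reader to Section 6 for visit procedures, and Section 6.1 does call for the interview. An eligible patient who later crosses either threshold has by definition changed since baseline, so the Section 6.1 condition largely overlaps with Section 3.1. Section 7.6.3 describes analysis and does not instruct sites. Section 1.5 reports no evidence so far of adverse effects on mood.

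Most of this stands, and it lowers the risk. It does not remove the contradiction. The Visit 3 to 5 instructions never mention the prompt, and a site that receives it still has a schedule footnote saying that the interview is not mandatory. That sites work mainly from the schedule is an inference; the documents do not say so.

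Three stronger readings are tempting, and the documents do not support them:
- **Every patient is affected at Visit 6.** No PHQ-9 is scheduled there, so the Section 3.1 condition has no scheduled score to act on. What remains is the discretionary route, on which Section 3.1 and the Visit 6 text agree.
- **Treatment arms cannot be compared on the C-SSRS.** No between-arm comparison of post-baseline results is planned. Even under Section 3.1 only triggered patients, or those judged to need it, are interviewed. The trial is double-blind, and nothing suggests that omissions would differ by arm. The supportable statement is that the listing could be incomplete.
- **A patient at risk could not be withdrawn without the interview.** Criterion 5 would lack an input, but criterion 3 (sponsor decision, including for safety) and criterion 4 (clinically significant event considered related to study drug) remain available.

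**Conclusion.** The point holds as an internal contradiction: the text is wrong as written. The core conflict is Section 3.1 against footnote 7, echoed in Section 7.6.3. Section 6.1 adds inconsistent verbs and an unquantified condition. For a patient who screens positive at Visit 3, 4 or 5, omitting the interview complies with footnote 7 and deviates from Section 3.1.

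The size cannot be given as a number. It is limited to patients who meet either PHQ-9 threshold at those three visits, and the documents give no expected frequency; it could be few or none. The practical risk further assumes that a site follows the footnote over Section 6.1 and does not act on the LogPad prompt. The correction is worth making because it concerns patient safety and the rule should be auditable. The documents do not show that interviews would commonly be missed.

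**What to change.** Reconcile Section 3.1, Section 6.1 (Visits 3 to 5), Section 7.6.3 and footnote 7 of Table 13-1 so that one trigger and one verb appear throughout. Where Visit 3 and withdrawal criterion 5 refer to Section 13.2, either put the trigger there or redirect the reference to the place that states it. Mention the LogPad prompt in the visit instructions, so that its standing relative to the rule is clear. Check that the Visit 6 text, where no PHQ-9 is scheduled, is consistent with whichever rule is kept. Which rule that is, and any threshold in it, is for the sponsor and medical monitor to decide.

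The cost is wording in an amendment. Removing the contradiction needs no added visit and no change to the sample size or the efficacy analysis.

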13.2 Appendix 2: Evaluation Instruments

13.2.1 Clinical Global Impression of Change (CGIC)

This patient-completed questionnaire is often referred to as PGIC (Patient Global Impression of Change). The following questions will be asked after the patient has completed the PEP at the final visit:

Compared to the start of the study, would you describe your premature ejaculation problem as:

-3 = Much worse

-2 = Worse

-1 = Slightly worse

0 = No change

1 = Slightly better

2 = Better

3 = Much better

Compared to the start of the study did you experience a meaningful change in the time you took to ejaculate (cum)? (Yes/No)

Compared to the start of the study did you experience a meaningful change in your level of distress related to your premature ejaculation? (Yes/No)

13.2.2 Premature Ejaculation Profile (PEP)

1. Over the past month, was your control over ejaculation during sexual intercourse:

1 – Very Poor 2 – Poor 3 – Fair 4 – Good 5 – Very Good

2. Over the past month, was your satisfaction with sexual intercourse:

1 – Very Poor 2 – Poor 3 – Fair 4 – Good 5 – Very Good

3. Over the past month, how distressed were you by how fast you ejaculated during sexual intercourse:

1 – Extremely 2 – Quite a bit 3 – Moderately 4 – A little bit 5 – Not at all

4. Over the past month, to what extent did how fast you ejaculated during sexual intercourse cause difficulty in your relationship with your partner:

1 – Extremely 2 – Quite a bit 3 – Moderately 4 – A little bit 5 – Not at all

Additional Question

5. Over the past month, how bothered were you by how fast you ejaculated during sexual intercourse:

1 – Extremely 2 – Quite a bit 3 – Moderately 4 – A little bit 5 – Not at all

Patient Global Impression of Severity (PGIS)

This questionnaire will be completed after the patient has completed the PEP.

How would you rate your premature ejaculation (PE) now? 1 No PE (none), 2 Mild 3 Moderate 4 Severe

13.2.3 International Index of Erectile Function (IIEF)

These questions ask about the effect your erection problems have had on your sex life **over the past 4 weeks**. Please answer these questions as honestly and as clearly as possible. Please answer every question by checking the appropriate box. If you are unsure about how to answer, please give the best answer you can.

In answering these questions, the following definitions apply:

* **Sexual intercourse**

Is defined as sexual penetration of the partner.

